1.3 Investigational Device

Silver diamine fluoride (SDF) is a **Category B low risk device**. It is a clear liquid, used for topical oral application on sensitive dentinal lesions to reduce sensitivity; on carious lesions to arrest decay; and on pits and fissures to prevent caries. Application is eligible for Medicaid coverage in some states.

1.4 Research Risks & Benefits

1.4.1 Risk of Investigational Device

The only known risks are allergies to silver and short-term (3-7 day) irritation from dripping on gingiva or epithelium. However oral health professionals working in this study will be trained on the proper techniques to avoid risks. All students with a silver allergy will be excluded from participating. The application of silver diamine fluoride may discolor any cavities resulting in a brown or black color. This color change indicates that the cavity has stopped growing. If accidental skin contact occurs it can cause a temporary light brown staining to the lips, cheeks, or permanent staining to clothing. For stain removal to the skin, soap and water are applied immediately. The same procedure is applied for cleaning clothes.

1.4.2 Other Risks of Study Population

1.4.2.1 Fluoride varnish

Children that have a nut allergy. Some fluoride varnish products contain pine nuts as an ingredient in their varnish resin formula. There are 2 fluouride varnish products being used in this study. The first product is called FluoroDose® and will not contain pine nuts as an ingredient. This product will be used for children that have a nut allergy. The second fluoride varnish product is called PreviDent® and will be used on children that do not have a nut allergy. These products are listed in section 5 under Study Device.

1.4.2.2 COVID-19

Care follows WHO guidance for essential, aerosol-free care. 2. The care is standard of care, based on American Dental Association guidelines. 3. Care

delivery follows current CDC guidelines for PPE. 4. Our subject population does not include categories of individuals currently known to be at greater risk of serious COVID-19 consequences.

In school and community-based programs have unique characteristics that warrant specific infection prevention considerations due to risk for exposure to COVID-19. **Enhanced precautions** are in place to avoid transmission of SARS Cov-2 in school and community-based settings.

All New York University College of Dentistry Health Care Personnel (NYUCD HCP) are required to get COVID-19 diagnostic PCR tests within 14 days prior to returning to work and submit verification, be tested every 14 days and complete the NYU daily screener. Any NYUCD HCP who fails on the "screener pass" will automatically be referred to the NYU COVID prevention & response team and will not report to work.

All clinical staff will wear personal protective equipment consistent with CDC, DOH, FDA and NYU Dentistry guidelines.

NYUCD HCP will be conducting all study related procedures at all locations. NYUCD HCP will wear PPE based on current NYU Dentistry guidelines. PPE is listed below:

- 1. Disposable gowns
- 2. Disposable gloves
- 3. N95 respirator that have been fit tested for a specific respirator and shall be disposed of at the end of each clinical day
- 4. Level 3 surgical masks
- 5. Goggles
- 6. Face Shields
- 7. Bonnets
- 8. Booties

Gloves are changed between patients. Goggles and face shields are disinfected with an EPA registered intermediate level surface disinfectant between patients. All dental chairs, stools and touch surfaces are disinfected with an EPA registered intermediate level surface disinfectant at the beginning of each day, prior to and after treating patients, and at the end of the day.

All NYUCD HCP including supervisory professionals will ensure that care is provided and overseen in a way that maximizes benefits while avoiding harm to personnel, students and parents/guardians from potential exposure to COVID-19 infection.

1.4.3 Potential Benefits

There are three distinct benefits.

1. The benefit to all participants is that they will receive either primary or primary and secondary caries prevention once or twice yearly. The expectation is that both the simple and complex will reduce caries by 50% to 80%.

- 2. If, as we propose, simple prevention is as effective as complex, and simple prevention takes approximately 1/4 the time and 1/4 the cost of complex prevention, its use will increase access to effective care.
- 3. The methods to be applied and the outcomes identified both address national Healthy People 2020 goals.

Ultimately, evidence-based changes in knowledge, attitudes and practice among all patient and stakeholder partners will help reduce the continually high burden of caries in children, particularly among minority and low-SES children. Improved outcomes data should increase support for the sustainability of ongoing and new caries prevention programs at both a local and national level. The benefits to society include improved oral health for our children that is sustained by a system of preventive care that is more clinically and cost effective than the current method of care.

Numerous efficacy trials demonstrate the benefits of complex preventive dental care, which has far-reaching effects on physical and emotional health, nutrition, social interactions and employability. However, numerous barriers still exist to improvements in child oral health: an already-existing global and national burden of caries; the burden of disease in NYC; the social burden of disease, particularly affecting academic performance and psycho-social development; barriers to office-based care⁹; economic incentives to support treatment rather than prevention; the reduced efficacy of treatment to prevention; and large variation in care without outcome measures of effectiveness.

Without data to support the effectiveness of preventive oral health care, we predict that two things will occur (depending on state and local values and circumstances): 1) the current helter-skelter implementation of well-meaning but ineffective programs will continue; and/or 2) there will be an extinction of those public caries prevention programs that are truly effective.

From a national perspective, our preliminary data suggest that a school-based caries prevention program may represent the first program that exceeds the goals of *Healthy People 2000*. If this happened, it would be transformative. This information would: 1) set the stage for broader dissemination within NYC and other metropolitan areas; and 2) stimulate implementation tests of other "place-based" caries prevention programs for other populations (e.g.: mothers, elderly, etc.), in locations where people learn, work, play, and pray.

Long term, we believe that children (and adults) with improved oral health will be better prepared to learn, thrive and improve their social and economic opportunities. These important accomplishments would be one step in reducing social inequalities. The proposed school and community-based, cluster, randomized controlled trial, comparing two evidence-based caries prevention protocols, will address and potentially obviate all of the identified gaps.

2 Study Objectives

2.1 Primary Objective

To determine if simple prevention is non-inferior to complex prevention for caries arrest and longitudinal caries prevention.

2.2 Secondary Objective(s)

To compare the effectiveness of simple prevention when provided twice yearly versus once yearly.

To determine if children receiving either simple prevention or complex prevention will have reduced school absence and higher academic performance when compared to matched students in non-participating schools.

To determine if children receiving simple prevention or complex prevention will have reduced dental service use and costs in Medicaid when compared to matched students in non-participating schools.

3 Study Design

3.1 General Design

This is a pragmatic cluster randomized non-inferiority controlled trial comparing the clinical effectiveness of two caries prevention protocols. The study consists of three groups. Two groups will be randomly assigned at the school level to receive either simple or complex prevention provided twice yearly. A third group will be selected to receive simple prevention only, provided once yearly.

A total of 76 elementary schools will be selected from interested schools in New York City, identified via letters and phone calls to school principals. For groups (1) and (2) 30 elementary schools will be randomized to receive simple prevention twice per year and 30 elementary schools will be randomized to receive complex prevention twice per year. For group (3), 16 elementary schools will be selected to receive simple prevention once per year.

Beginning in the first year of the study, a total of 30 schools will be randomized (15 schools receiving simple prevention and 15 receiving complex prevention) to receive prevention twice per year consenting children will be followed over five years. In Year 2, 30 additional schools will be randomized to receive either simple or complex prevention twice per year. Consenting children will be followed over four years. Also in Year 2, an additional 16 schools will be selected to receive simple prevention once per year, and consenting children will be followed over four years. Also in Year 2, an additional 16 schools will be selected to receive simple prevention once per year, and consenting children will be followed over four years. Starting in year 3, all care will be provided by NYUCD HCP, in school, at community-based locations, or at NYUCD. Starting in year 5, NYUCD licensed dentists, dental hygienists, nurses, and/or advanced level dental hygiene students supervised by licensed dental professionals will provide care to participating students, in school, at community-based locations, or at NYUCD.

The inclusion criteria for the schools enrolled in groups (1) and (2) include: A Hispanic/Latino population of at least 50% and a free and reduced lunch population of at least 80%. The remaining racial/ethnic and socioeconomic of the schools beyond these criteria can include children from any race/ethnicity and economic background. The inclusion criteria for schools in group (3) include any elementary school in New York City. Schools in group (3) will be balanced to ensure representation from every primary race/ethnic group and from all socioeconomic tertiles.

The impact of COVID-19 has greatly impacted our in school-based cavity prevention approach. Elementary schools have closed, delayed in opening and will either allow students to return to schools part-time under a blended learning model or will learn at home remotely full-time. This has impacted our ability to provide preventive services in some or possibly all of our schools. In order to continue to provide these services, our community engagement administrator will reach out to those schools where we cannot currently provide in school care, seek their guidance in helping to identify and connect with local community-based organizations in their area and then telephone these local organizations to discuss participation in the research study.

Once an alternate community-based location has been identified and is interested in participating, our HCP will meet with the community organization staff to review COVID-19 safety precautions at the community-based location, clinical protocols, room size and safe distancing requirements. NYUCD HCP will fill out the Caried*Away* COVID-19 community-based location does not meet the requirements listed in the checklist, the NYUCD HCP will notify the Principal Investigator that the site is not an acceptable location for providing safe care.

If the community-based location meets the requirements of the Caried*Away COVID-19* community-based checklist and wishes to participate, the NYUCD HCP will review the Memorandum of Understanding (MOU). As community organizations are identified and sign an MOU we will submit their name and location to the IRB.

All clinical personnel will wear personal protective equipment consistent with CDC, DOH, FDA and NYU Dentistry guidelines.

NYUCD licensed dentists, dental hygienists, nurses, and/or advanced level dental hygiene students supervised by licensed dental professionals will provide care to participating students at all locations. All clinical personnel providing care will wear PPE based on current NYU Dentistry guidelines. PPE is listed below:

- 1. Disposable gowns
- 2. Disposable gloves
- 3. N95 respirator that have been fit tested for a specific respirator and shall be disposed of at the end of each clinical day
- 4. Level 3 surgical masks
- 5. Goggles
- 6. Face Shields
- 7. Bonnets
- 8. Booties

Gloves are changed between patients. Goggles and face shields are disinfected between patients. All dental chairs, stools and touch surfaces are disinfected at the beginning of each day, prior to and after treating patients, and at the end of the day.

Caried*Away* school COVID-19 Checklist: The first day of the school visit the NYUCD HCP will review the school's policies for prevention of coronavirus transmission among students, staff and faculty using the Caried*Away* School COVID-19 Checklist. If there is any reason to believe that schools policies would put NYUCD HCP or students at risk, the NYUCD HCP Dental will contact the Principal Investigator to determine the appropriate course of action.

Consenting students in participating schools will receive care in a school, at a community-based location, or at NYUCD. Randomization will be done by computer and remain in effect during the duration of the trial. Care will be provided in a school, community-based locations or at NYUCD according to the group selection as described above. Participants in their first and second year will contribute data to evaluate caries arrest. We will follow them longitudinally to evaluate prevention of new caries. The total expected school enrollment for the clinical and community components of the study is 76 schools.

Hypotheses and Interventions: We will test the primary hypothesis that school or communitybased "simple" caries arrest and prevention provided twice yearly is equally effective (noninferior) as school or community-based "complex" caries arrest and prevention provided twice yearly.

- "Simple" prevention is defined as fluoride varnish, silver diamine fluoride, fluoride toothpaste and oral hygiene instruction.
- "Complex" prevention is defined as traditional sealants, interim therapeutic restorations, fluoride varnish, fluoride toothpaste and oral hygiene instruction.

Table 1. Comparison simple and complex prevention on primary and secondary caries
reduction ^{***} .

		Complex Prevention			Simple Prevention			
Focus:	Intervention:		Fluoride Varnish		Interim Therapeutic Restoration	Toothpaste	Varnish	Silver Diamine Fluoride
1° Prevention	Smooth surface	25% ¹	40%²			25% ¹	40%²	
	Pits and fissure			80% ³				80% ⁵
2° Prevention	Arrest current caries				80%4			80% ⁵

* Efficacy estimates of caries reduction from systematic reviews of human randomized controlled trials.

**References: 1.¹¹⁻¹²; 2.¹³; 3.¹⁴⁻¹⁶; 4.^{14, 17-19}; 5.²⁰⁻²²

Both types of care will be provided to all children with active informed consent in grades PK - 8 (ages 5 – 14). Participating schools will be randomized or selected at the school level to receive either simple or complex prevention. All participants in a given school, community-based location, or at NYUCD will receive the same prevention as randomized. At the beginning of each school year, all students in grades PK - 8 will be given a personalized pre-populated principal recruitment letter, the parent/guardian alternate location recruitment letter, the parent/guardian informed consent form.

Electronic informed consent forms will be distributed to parents/guardians of new students who have not previously consented to see if they wish to have their child participate. Electronic informed consents can be distributed by the schools using whichever existing method the school uses for mobile phone contact, in emails, or on the school's social media page in the following ways:

- 1. NYU CariedAway Website URL by selecting "registering your child"
 - 1) English
 - https://dental.nyu.edu/faculty/epidemiology-health-promotion/pcori-grant.html
 - Short URL: https://dental.nyu.edu/pcori
 - 2) Spanish

https://dental.nyu.edu/faculty/epidemiology-health-promotion/pcori-beca.html

- 2. Hyperlinks in English and Spanish
 - English language eICF: https://is.gd/CariedAwayNYC
 - Spanish language eICF: https://is.gd/CariedAwayNYC_SP
- 3. CariedAway email toolkit in English and Spanish

The parent or legal guardian fills out the eICF and uses 'scratch' method (mouse, stylus, or finger) to sign and then returns the completed ICF via REDCap.

The study administrator will then cross-reference the OSIS number in the original .csv file which was provided to us at the beginning of each school year by the NYC Department of Education, and verify that the correct OSIS number was provided correctly by the consenter.

The study administrator then uploads all of the informed consent PDF's to NESS via the secure and password protected ShareFile link listed below:

• https://nedental.sharefile.com

NESS then uploads each student's eICF to their electronic dental record in the iPad.

Examination, preventive care, and data collection by a proprietary secure electronic health record will be provided and collected up to 5 years, and all children in a given school will receive the same preventive care at the same frequency either at the school, at a community-based location or at NYUCD. Participants in their first and second years will contribute data to evaluate caries arrest, and then they will be followed longitudinally within schools. 50% of children ≥ 8 years old will be assessed with a validated quality of life instrument, and all children will receive a comprehensive oral examination at each visit. We will also test the secondary hypotheses that prevention: improves school performance and is equally effective given once per year as twice per year.

3.2 Primary Study Endpoints

Caries arrest and prevention will be determined at each visit. The primary end point for caries arrest will be at 2 years, and follow on to termination of trial determine the length of time that caries remains arrested. The primary end point for caries prevention will be at 3 years, and follow on to termination of trial to determine stability of prevention.

Presence / absence of caries is assessed by visual/tactile methods. Sound tooth surfaces appear white and smooth. Active caries appear brown and soft. Arrested caries appear dark brown or black and hard.

For clinical assessment, we will train and standardize clinicians using validated criteria implemented by the Centers for Disease Control and Prevention (CDC) in the National Health and Nutrition Examination Surveys (NHANES). Training and validation were developed and documented by our Colleague, [name], while at the CDC and field tested in the examination of special athletes^{23,24}. Training and standardization of these examiners implement the World Health Organization guidelines^{25,26}.

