6.1.6 Examination and Diagnosis

Each program will use password-protected Apple iPads with electronic dental records pre-populated with demographic information of all students with informed consent. Student lists on the Apple iPads will be used to: collect students during the care delivery days; record clinical findings and care delivered; and generate take home forms (see below). On the scheduled care days, we will provide a gentle toothbrush cleaning, oral hygiene instruction, a toothbrush and fluoridated toothpaste. We will also carry out an examination and provide preventive care.

The examination will include a soft tissue inspection and an assessment of all primary and permanent teeth to determine the presence/ absence of decay (active or arrested), missing, filled, or sealed surfaces on all teeth.

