6.1.7 Prevention

Both simple and complex care regimens provide both primary and secondary caries prevention. The goal of primary prevention is to prevent or delay the initial carious lesion using: 1) fluoride varnish for smooth surfaces (simple and complex prevention); and 2) either silver diamine fluoride (simple prevention) or sealants (complex prevention) for pits and fissures. The goal of secondary prevention is to arrest caries *in situ*, and prevent disease progression. This is accomplished with silver diamine fluoride (simple prevention) or interim therapeutic restorations (complex prevention).

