7.2 Statistical Methods

For caries arrest, we will first determine the per-patient proportion of carious lesions treated with simple versus complex prevention that stayed arrested throughout the length of the study. The percentage of arrested caries (at the child level) will be modeled using multilevel binomial regression. Our noninferiority margin, δ , is set at 10%. Our null hypothesis is that simple prevention is not inferior to the complex prevention by at least δ : π_{simple} - $\pi_{\text{complex}} \ge \delta$. Our alternative hypothesis is that π_{simple} - $\pi_{\text{complex}} < \delta$. We will use differences in effect sizes as estimated by confidence intervals to determine clinical non-inferiority of the two prevention methods. For the prevention of new caries, we will use generalized estimating equations (GEE) with a logit link (caries prevalence) and a negative binomial link (caries incidence), assuming an exchangeable correlation matrix, to evaluate longitudinal effects of comprehensive care untreated decay. We will identify the number of teeth at risk for each child during each follow-up interval and determine the number of those teeth in which new caries is observed at the examination that ends that interval. Primary teeth lost in each interval and new permanent teeth will not contribute to data for that interval. To explore non-linear trends in untreated decay between simple and complex prevention, we will use generalized additive models (GAMs) with non-parametric smoothers. Longitudinal effects of simple and complex prevention on academic outcomes, compared to untreated children, will be analyzed using propensity score-matching and multilevel modeling. First, we will estimate propensity scores for each participant at baseline, establishing the probability of treatment assignment conditional on observed covariates (e.g., prior academic performance). Propensity scores will be used to match treatment students to students not receiving treatment, considering multiple forms of matching
such as nearest neighbor and caliper. Treated students and matched comparators will then be analyzed using multilevel mixed effects linear regression (for academic achievement) and Poisson regression (for school absences).

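### The caries-arrest definition is not arm-neutral: silver diamine fluoride can supply its colour feature, and restored or sealed lesions have no scoring rule

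*Combined protocol and SAP*

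**What the plan says.** All references are to the combined protocol and SAP.

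- **Endpoint (3.2).** Caries arrest is a primary endpoint, assessed at 2 years. "Presence / absence of caries is assessed by visual/tactile methods". Besides sound surfaces, two states are described: "Active caries appear brown and soft" and "Arrested caries appear dark brown or black and hard".
- **Effect of the simple-arm product (1.4.1).** "The application of silver diamine fluoride may discolor any cavities resulting in a brown or black color". The text continues: "This color change indicates that the cavity has stopped growing".
- **Treatment of existing lesions (6.1.7, 6.2.2).** The simple arm uses silver diamine fluoride (SDF). For the complex arm, 6.1.7 names interim therapeutic restorations, and 6.2.2 describes glass ionomer sealant placed on asymptomatic carious lesions.
- **Examination codes (6.1.6).** The examiner records presence or "absence of decay (active or arrested), missing, filled, or sealed surfaces on all teeth".
- **Outcome variable (7.2).** The analysis uses the "per-patient proportion of carious lesions treated with simple versus complex prevention that stayed arrested throughout the length of the study", modelled at child level against a 10-point margin.
- **Who scores (5.7, 6.2, 6.5.2).** The examination is part of each care visit. Clinicians are unblinded, and each team delivers one arm's care only. The analysts are blinded. No separate or masked examiner is described.

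**The concern.** A non-inferiority comparison needs an outcome that means the same thing in both arms. Here it may not, for two reasons.

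First, the arrest definition has a colour feature and a hardness feature. In the simple arm the product can produce the colour, and 1.4.1 interprets that change as a sign of arrest. In the complex arm, a hard lesion exposed when a restoration is lost must show the dark colour without that help.

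Second, while the material is in place, a complex-arm lesion carries a filled or sealed code. The plan does not say whether such a lesion counts as arrested, as not arrested or as missing. For those lesions the numerator of the 7.2 proportion is undefined.

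Both gaps are filled in practice by clinicians who know the arm and work in only one. At stake is the arrest conclusion: a scoring difference between arms can hide a true deficit or make equivalent care look inferior.

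**Working it through.** **1. Reproduce the plan's figure.** Inputs from 7.1: arrest 20% in both arms, margin 10 points, alpha 5%, power 80%, intraclass correlation 0.10, 235 children per school.

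- n per group = (1.645 + 0.842)² × (0.20 × 0.80 + 0.20 × 0.80) / 0.10² = 197.8, so 198 and 396 in total. This matches, with alpha read as one-sided 5%. One-sided 2.5% gives 252 and does not match.
- Design effect = 1 + (235 − 1) × 0.10 = 24.4, and 396 × 24.4 = 9,662. This matches.

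The sample-size arithmetic is therefore not at issue. The effective size used below is 198 per group.

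**2. How much the missing rule can matter.** Let a be the mean per-child proportion of complex-arm treated lesions that are uncovered and scored arrested, and c the mean proportion under an intact filled or sealed surface.

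- Covered counted as arrested: a + c.
- Covered counted as not arrested: a.
- The two codings differ by c.

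The documents give no value for c, which could lie anywhere from 0 to 100%. Once c reaches 10%, the choice of coding alone moves the comparison by the full margin.

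**3. What a scoring shift does to the test.** The shift b is my assumption, because the documents give no misclassification rate. The test is the usual one for a success proportion: declare non-inferiority when the lower one-sided 95% bound for simple minus complex lies above −10 points. I use a normal approximation and a binary outcome per child.

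*Shift towards simple, true deficit exactly at the margin (complex 20%, simple 10%).* Observed simple arrest is 0.10 + b, and P(declare) = Φ(b/SE − 1.645). For b = 0.05, SE = √[(0.20 × 0.80 + 0.15 × 0.85)/198] = 0.0381, so P = Φ(1.312 − 1.645) = 37.0%.

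*Shift towards complex, arms truly equal at 20%.* Observed complex arrest is 0.20 + b, and power = Φ((0.10 − b)/SE − 1.645). For b = 0.05, SE = √[(0.25 × 0.75 + 0.20 × 0.80)/198] = 0.0419, so power = Φ(1.194 − 1.645) = 32.6%.

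| Assumed shift (points) | False non-inferiority, shift towards simple | Power, shift towards complex |
|---|---|---|
| 0 | 5.0% | 80.0% |
| 2 | 13.6% | 62.2% |
| 5 | 37.0% | 32.6% |
| 8 | 65.0% | 12.0% |

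At one-sided 2.5%, the 5-point row becomes 25.9% (from 2.5%) and 22.2% (from 70.1%). With the 14,100 expected children, the effective size is 7,050/24.4 = 289 per arm. At one-sided 5%, the 5-point row is then 47.6% and 42.0% (power from 91.3%).

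**4. What a shift would take.** If the true simple-arm rate were 10% and one in nine non-arrested SDF lesions were scored arrested, the observed rate would be 0.10 + 0.90/9 = 0.20, and the whole deficit would disappear. This too is conditional: the documents do not suggest that such misreading occurs at that rate.

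**The case against.** The strongest reply is that the definition already protects itself. It requires hardness as well as colour, the method is tactile as well as visual, and active caries is also described as brown, so hardness is what separates the two states. A reader might infer that an SDF stain is enough to score a lesion as arrested. The text does not support that: a stained soft lesion fails the written definition, and no section says that staining hardens a lesion. Section 1.4.1 is a risk description, not a scoring instruction.

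A reader might also infer that the bias must favour simple prevention. That would hold only if covered lesions counted as not arrested. If filled or sealed surfaces counted as arrested, the shift would favour complex and make non-inferiority harder to show; if they were missing, the direction is unknown. That a covered lesion can be neither seen nor felt is a natural inference for a visual and tactile method, but the plan does not state it.

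The plan also has safeguards: training to national survey criteria and international guidelines (3.2), yearly calibration, and site visits that monitor caries diagnosis (6.6). Masking would be difficult when one arm has stained lesions and the other has restorations.

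These replies remove the claim of a proven, one-directional bias. They do not supply a rule for covered lesions, and they do not make the colour feature equally attainable in both arms. Training standardises examiners to a rule, but these documents contain no rule for stained, covered or exposed lesions. Whether the cited criteria contain one cannot be checked here.

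**Conclusion.** The point holds as a defect of endpoint definition. The arrest rule is not arm-neutral, it gives no scoring for restored or sealed lesions, and unblinded single-arm teams apply it. Two analysts following this plan could code the same filled surfaces in opposite ways.

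The direction and size of any bias cannot be derived from the documents. The table shows sensitivity under assumed shifts, not an estimate of what will happen. It rests on the plan's 20% arrest rate, its 10-point margin, a one-sided 5% test, an effective 198 per group and a binary simplification of the per-child proportion.

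A reader might extend this to the whole primary comparison. That is not supported: prevention of new caries is a separate primary endpoint with its own analysis. Because arrest is a primary non-inferiority endpoint, its scoring should be settled before it is analysed.

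**What to change.** Amend 3.2 and 7.2 to use one treated-lesion outcome in both arms, assessed at the 2-year visit. Section 7.2 currently refers to the whole length of the study.

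- **Criterion.** Hardness decides. Colour is recorded but not used.
- **Failure.** Soft (active) decay on the surface that was carious at baseline, or at the margin of its restoration or sealant; or a filling or extraction of that tooth that is not in the study's own care record.
- **Not a failure, in either arm.** Study-delivered reapplication or replacement.
- **Lost restoration or sealant.** The exposed lesion is scored on hardness only.
- **Naturally exfoliated primary teeth.** One stated rule, identical in both arms. Section 7.2 has a rule for lost primary teeth only in the new-caries analysis.
- **Sensitivity analyses.** Code lesions under intact filled or sealed surfaces as arrested, as not arrested and as missing, and report whether the non-inferiority conclusion survives all three.

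The cost is small: revised wording in two sections, an added item in the calibration already planned in 6.6, and a check of each filling or extraction against the study's care record to separate study care from outside care. Section 6.1.6 already provides for the surface codes and for recording care delivered. The downside is that arrest under an intact restoration is presumed rather than observed, which is why the three codings are needed.
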